3.3 Early Withdrawal of Subjects

3.3.1 Criteria for removal from study

Insert subject withdrawal criteria (e.g., safety reasons, failure of subject to adhere to protocol requirements, subject consent withdrawal, disease progression, etc.).

Subject participation will be discontinued by recommendation of the team physician ([name]) if the subject experiences excessive pain during stimulation (>5/10), excessive tendon elongation (>3 cm), gapping at the repair site (>5 mm) or other AEs. Participants will also be removed if the outcomes from the repair surgery require patients to deviate from the standard rehabilitation protocol. An additional criteria include failure of the subject to adhere to the protocol and subject consent withdrawal.

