3.3.2 Follow-up for withdrawn subjects

Describe when and how to withdraw subjects from the study; the type and timing of the data to be collected for withdrawal of subjects; whether and how subjects are to be replaced; the follow-up for subjects withdrawn from investigational treatment.

Data collected up to the time of withdrawal may be used in the study. Subjects will be recruited until the desired number of participants with complete data points is reached. Subjects who experience AEs that are potentially related to the intervention will be followed via phone call or email to obtain information on how the AE resolves.

Participants who experience any of the above mentioned AEs will be followed up until resolved or stabilized.

Subject will be asked for consent to be contacted for possible future studies. Withdrawn subjects will be contacted if new information is available concerning the methods and techniques used in the study.

The subjects who withdraw from the study will not be replaced.

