10.0 Risks

List the reasonably foreseeable risks, discomforts, hazards, or inconveniences to the subjects related to the subjects' participation in the research. Include as may be useful for the IRB's consideration, a description of the probability, magnitude, duration and reversibility of the risks. Consider all types of risk including physical, psychological, social, legal, and economic risks. Note: Loss of confidentiality is a potential risk when conducting human subject research.

- If applicable, indicate which procedures may have risks to the subjects that are currently unforeseeable.
- If applicable, indicate which procedures may have risks to an embryo or fetus should the subject be or become pregnant.
- If applicable, describe risks to others who are not subjects.

Risk of Randomization: You will be assigned to a treatment program by chance. The treatment you receive may prove to be less effective or to have more side effects than the other research treatment(s) or other available treatments.

Heel-rise test: The heel-rise testing may cause local tendon pain. The subjects will be informed that if they have a pain level above a 5/10 they should inform the evaluator, stop the test, and avoid strong physical activity for 1 or 2 days.

NMES usage: The device used for this test is FDA approved. There is a minimal risk of infection. Discomfort during and muscle soreness after usage lasting a few days after the test may be experienced. Skin irritation caused by the adhesive pads may also occur. Excessive pain might occur during stimulation, even at the recommended settings. Subjects will be instructed to gradually increase the stimulation intensity up to the recommended level by PT. Subjects will be instructed to contact the research team if the excessive pain occurs at or below the recommended intensity.

Tendon healing: Re-injury of the tendon is also a potential risk. The rate of tendon re-rupture in standard therapy is estimated between 2% and 5% [64]. Gapping or non-healing of the tendon have also been observed in regular therapy. These adverse events may be observed in the participants participating in the study. Statistical analysis will be performed to determine if the risk of these adverse events is higher in the intervention group compared to standard therapy.

Additional Risks

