18.2 Recording of Adverse Events

Address the frequency and process for eliciting adverse event information from research subject, e.g., "Research subjects will be routinely questioned about adverse events at study visits."

In the response, incorporate the following as written:

All adverse events (serious or non-serious) and abnormal test findings observed or reported to study team believed to be associated with the study drug(s) or device(s) will be followed until the event (or its sequelae) or the abnormal test finding resolves or stabilizes at a level acceptable to the investigator.

An abnormal test finding will be classified as an adverse event if one or more of the following criteria are met:

- The test finding is accompanied by clinical symptoms
- The test finding necessitates additional diagnostic evaluation(s) or medical/surgical intervention; including significant additional concomitant drug treatment or other therapy

NOTE: Simply repeating a test finding, in the absence of any of the other listed criteria, does not constitute an adverse event.

- The test finding leads to a change in study drug dosing or discontinuation of subject participation in the clinical research study
- The test finding is considered an adverse event by the investigator.

Research subjects will be routinely evaluated by research team (part of the study team) during visits of the standard rehabilitation protocol.

All adverse events (serious or non-serious) and abnormal test findings observed or reported to study team believed to be associated with the study device(s) will be followed until the event (or its sequelae) or the abnormal test finding resolves or stabilizes at a level acceptable to the investigator.

An abnormal test finding will be classified as an adverse event if one or more of the following criteria are met:

- The test finding is accompanied by clinical symptoms
- The test finding necessitates additional diagnostic evaluation(s) or medical/surgical intervention
- The test finding is considered an adverse event by the investigator.

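### No section looks for new adverse events after a participant is removed, although removal is triggered by poor healing and the safety comparisons and stopping rules rest on event counts

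*Combined protocol and SAP*

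**What the plan says.** **Removal.** Section 3.3.1: "Subject participation will be discontinued by recommendation of the team physician" for "excessive pain during stimulation (>5/10), excessive tendon elongation (>3 cm), gapping at the repair site (>5 mm) or other AEs". It also lists failure to adhere, withdrawal of consent, and surgical outcomes that force a departure from standard rehabilitation. Section 9.1 adds removal when the physician changes the rehabilitation protocol or prescribes a further intervention such as surgery.

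**After removal.** Section 3.3.2 has three relevant statements:
- "Data collected up to the time of withdrawal may be used in the study".
- "Subjects who experience AEs that are potentially related to the intervention will be followed via phone call or email", to learn how the event resolves.
- "Participants who experience any of the above mentioned AEs will be followed up until resolved or stabilized".

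Section 18.2 says that adverse events and abnormal test findings "believed to be associated with the study device(s) will be followed until the event (or its sequelae"), or the finding, has resolved or stabilised.

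**How events are otherwise found.** Sections 9.1 and 9.3 collect AEs at study visits. Sections 9.1 and 18.2 also mention monitoring during standard-of-care rehabilitation visits.

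**What the counts are used for.** Sections 8.3 and 9.7 compare AEs between arms by an odds ratio with a 95% confidence interval. Section 9.8 suspends the study if that ratio is significant, and section 18.8 interrupts it if AE rates exceed those of standard care. On re-injury, gapping and non-healing, section 10.0 states: "Statistical analysis will be performed to determine if the risk of these adverse events is higher in the intervention group compared to standard therapy".

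**The concern.** Following a known event to its end is different from looking for the next one. Section 3.3.2 provides for the first only. The grounds for removal include early signs of a poorly healing tendon, so observation ends in people who are plausibly more likely than average to re-rupture. Tendon length is first imaged at week 6 (7.1, Table 3). Someone removed on that finding would have weeks 6 to 12 unobserved.

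The scope is also unclear. One sentence of 3.3.2 is limited to events potentially related to the intervention, a test that can hardly apply to a control participant without a device. The other refers back to events mentioned above, which could mean only those related events or the whole 3.3.1 list in both arms.

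Loss may also be uneven. Pain during stimulation can remove only NMES participants, and only that arm has a device regimen to adhere to. At stake is whether the safety comparison and the two stopping rules work on complete counts collected alike in both arms.

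**Working it through.** **1. Inputs.** 25 per arm (8.3). Attrition 10% (8.2). Re-rupture under standard care 5% (9.1), or 2% to 5% (10.0). Infection 2.8% and DVT 48% (9.1). The plan's arm size follows from its own figures: 22 / 0.9 = 24.4, rounded up to 25.

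**2. Expected counts per arm.**
- Re-rupture: 25 × 0.02 = 0.5 to 25 × 0.05 = 1.25.
- Infection: 25 × 0.028 = 0.7.
- DVT: 25 × 0.48 = 12, where a single missed event weighs much less.
- Attrition: 50 × 0.10 = 5 people in all. Section 8.3 ties this figure to missed visits and loss to follow-up, so it is only a guide to the number removed.

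**3. Odds-ratio rule (8.3, 9.7, 9.8).** For a of 25 NMES and c of 25 control events, OR = a(25 − c) / [(25 − a)c]. The lower limit is exp[ln OR − 1.96 × √(1/a + 1/(25 − a) + 1/c + 1/(25 − c))], with 0.5 added to each cell if one is zero.
- 7 vs 1: OR = 7 × 24 / (18 × 1) = 9.33; SE = √(1/7 + 1/18 + 1 + 1/24) = 1.114; lower limit 1.05.
- 6 vs 1: OR = 6 × 24 / (19 × 1) = 7.58; SE = √(1/6 + 1/19 + 1 + 1/24) = 1.123; lower limit 0.84.

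| Control events | Fewest NMES events that signal (lower limit) | One NMES event fewer |
|---|---|---|
| 0 | 7 (1.11) | 6 (0.90) |
| 1 | 7 (1.05) | 6 (0.84) |
| 2 | 8 (1.02) | 7 (0.83) |
| 3 | 10 (1.15) | 9 (0.96) |

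At each boundary one unrecorded NMES event removes the signal. These counts lie far above the expected number of re-ruptures, so the table bears on AEs counted together more than on re-rupture alone.

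**4. Rate rule (18.8).** Assume the rate is events divided by 25 in the NMES arm; the section does not say. Against 5%, two re-ruptures (2/25 = 8%) trip the rule and one (1/25 = 4%) does not. One infection (4%) exceeds 2.8%. Here a single unrecorded event can decide the outcome.

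**5. What differential removal could do (illustration).** Assumptions not in the documents: removal comes before re-rupture; those removed come from a high-risk fifth of the arm with k times the risk of the rest; all 25 stay in the denominator. With overall risk p, the low-risk rate is x = p / (0.2k + 0.8) and the observed risk is p − w·k·x, where w is the share removed.

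Example with p = 5% and k = 2: x = 0.0417 and kx = 0.0833. Removing 10% of NMES leaves 0.05 − 0.1 × 0.0833 = 0.0417. Removing 4% of controls leaves 0.0467. Observed OR = (0.0417/0.9583) / (0.0467/0.9533) = 0.89.

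| Removed, NMES / control | Equal true risk 5%: observed OR, k = 2 to 4 | True 10% vs 5% (OR 2.11): observed OR, k = 2 to 4 |
|---|---|---|
| 10% / 10% | 1.00 | 2.09 to 2.08 |
| 10% / 4% | 0.89 to 0.83 | 1.86 to 1.72 |
| 20% / 4% | 0.70 to 0.54 | 1.46 to 1.12 |

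At 5% risk and 10% removed, expected events lost are 25 × 0.1 × kx = 0.21 (k = 2) to 0.31 (k = 4) per arm. With equal removal the odds ratio barely moves, but events are still lost.

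**The case against.** A reader might infer that the relatedness limit itself biases the AE odds ratio. It does not. That limit governs how a known event is followed to resolution, and a recorded event counts in 8.3 and 9.7 whether or not its course is followed.

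A reader might also infer that the highest-risk participants drop out of the safety comparison. They do not: everything up to withdrawal, including the event that triggers removal, may be used. Only later events are lost.

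Nor do the documents show that the bias makes NMES look safer. They give no withdrawal rates by arm. Gapping and elongation can remove people from either arm, and nothing shows that those removed for stimulation pain are at high risk of re-rupture. If contact after removal is limited to related events, NMES participants may even be observed more completely, which would push the other way. One missed event is 1/1.25 = 80% of an arm's expected re-ruptures at 5%, but that ratio says nothing about how often an event is missed.

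The fairest defence is that a later event might come to notice anyway. On the wider reading of the second follow-up sentence, someone removed for gapping is followed until stable in either arm. Removed participants may also still attend rehabilitation visits. Both are possible. But nothing says that monitoring continues after removal or that events found that way enter the comparison, and section 2.1 allows rehabilitation at other centres. The gap is inferred from silence rather than from an explicit exclusion, yet 3.3.2 is where such a rule belongs.

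**Conclusion.** The point holds as an omission with an ambiguous scope. Section 3.3.2 follows existing events only, and no section provides for finding new ones after removal in either arm. Followed as written, re-ruptures, DVTs and infections after removal would not be counted in the 8.3, 9.7 and 10.0 comparisons or in the 9.8 and 18.8 rules.

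The expected loss is a fraction of an event per arm under the assumptions in step 5, but expected re-ruptures are themselves only 0.5 to 1.25 per arm, and one event can decide a rule at the margin. Uneven ascertainment is possible because some removal grounds fall only or mainly on NMES. Its direction and size cannot be determined from the documents. The illustrative odds ratios rest on assumed removal shares and relative risks and are not forecasts.

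**What to change.** In 3.3.2:
- Separate stopping NMES or leaving study procedures from leaving safety follow-up. The removal grounds themselves need not change.
- State one rule for both arms: every withdrawn participant who has not refused contact is phoned or emailed at the week-6 and week-12 time points still ahead and asked about re-rupture, further surgery, DVT, infection and skin irritation, whatever the relatedness.
- State that the sentence on following the events mentioned above applies to both arms.

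In 8.3 and 9.7, include these events by randomised arm, and report the number not reached in each arm rather than assuming that they were event-free. Leave the template wording of 18.2 as it is and add a cross-reference to 3.3.2.

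The cost is one or two short contacts for each of about five people (10% of 50), by the route 3.3.2 already names, and consent wording that allows it. The sample size does not change.

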4.0 Recruitment Methods

- Upload recruitment materials for your study in CATS IRB ([Error! Hyperlink reference not valid.](#)). **DO NOT** include the actual recruitment wording in this protocol.
- StudyFinder: If StudyFinder ([Error! Hyperlink reference not valid.](#)) is to be used for recruitment purposes, separate recruitment documents do not need to be uploaded in CATS IRB. The necessary information will be captured from the StudyFinder page in your CATS IRB study.

- Any eligibility screening questions (verbal/phone scripts, email, etc.) used when contacting potential participants must be uploaded to your study in CATS IRB (**Error! Hyperlink reference not valid.**).

[Do not type here]

4.1 Identification of subjects

Describe the source of subjects and the methods that will be used to identify potential subjects (e.g., organizational listservs, established recruitment databases, subject pools, medical or school records, interactions during a clinic visit, etc.). If not recruiting subjects directly (e.g., database query for eligible records or samples) state what will be queried, how and by whom.

StudyFinder:

- If you intend to use StudyFinder (**Error! Hyperlink reference not valid.**) for recruitment purposes, include this method in this section.
- Information provided in this protocol needs to be consistent with information provided on the StudyFinder page in your CATS IRB study.

For Penn State Health submissions using Enterprise Information Management (EIM) for recruitment, and for non-Hershey locations as applicable, attach your EIM Design Specification form on in CATS IRB (**Error! Hyperlink reference not valid.**). See “HRP-103- Investigator Manual, What is appropriate for study recruitment?” for additional information. **DO NOT** include the actual recruitment material or wording in this protocol.

Potential subjects will be identified when they become eligible for tendon rupture repair after a complete rupture.

4.2 Recruitment process

Describe how potential subjects first learn about this research opportunity or indicate as not applicable if subjects will not be prospectively recruited to participant in the research. Subject recruitment can involve various methods (e.g., approaching potential subjects in person, contacting potential subjects via email, letters, telephone, ResearchMatch, or advertising to a general public via flyers, websites, StudyFinder, newspaper, television, and radio etc.). **DO NOT** include the actual recruitment material or wording in this protocol.

[Do not type here]

4.2.1 How potential subjects will be recruited.

Clinicians who agree to collaborate in the study will hand a flyer to participants diagnosed a mid-portion Achilles tendon rupture and ask them if they want to be contacted to know more about the study. Those expressing interest will be contacted by a member of the research team.

4.2.2 Where potential subjects will be recruited.

4.2.3 Recruitment will occur in the Bone and Joint clinic in a private room within the clinic When potential subjects will be recruited.

Participants meeting eligibility requirements will be approached in the Bone and Joint Outpatient Clinic and presented with the study opportunity prior or shortly (within a week) to their planned surgery date.

4.2.4 Describe the eligibility screening process and indicate whether the screening process will occur before or after obtaining informed consent. Screening begins when the investigator obtains information about or from a prospective participant in order to determine their

eligibility. In some studies, these procedures may not take place unless HIPAA Authorization is obtained OR a waiver of HIPAA Authorization when applicable for the screening procedures is approved by the IRB. [For FDA regulated studies, consent for any screening activities would need to be obtained prior to screening unless specifically waived by the IRB.]

Eligibility and screening questions will be asked after obtaining verbal consent. Those questions have been included in the document "Eligibility and screening questions" submitted with application

5.0 Consent Process and Documentation

Refer to the following materials:

- The "HRP-090- SOP - Informed Consent Process for Research" outlines the process for obtaining informed consent.
- The "HRP-091- SOP - Written Documentation of Consent" describes how the consent process will be documented.
- The "HRP-314- Worksheet - Criteria for Approval" section 7 lists the required elements of consent.
- The "HRP-312- Worksheet - Exemption Determination" includes information on requirements for the consent process for exempt research. In addition, the CATS IRB Library contains consent guidance and templates for exempt research.
- The CATS IRB library contains various consent templates for expedited or full review research that are designed to include the required information.
- Add the consent document(s) to your study in CATS IRB (**Error! Hyperlink reference not valid.**). Links to Penn State's consent templates are available in the same location where they are uploaded. **DO NOT** include the actual consent wording in this protocol.

[Do not type here]

5.1 Consent Process:

Check all applicable boxes below:

- Informed consent will be sought and documented with a written consent form [Complete Sections 5.2 and 5.6]**
- Implied or verbal consent will be obtained – subjects will not sign a consent form (waiver of written documentation of consent) [Complete Sections 5.2, 5.3 and 5.6]**
- Informed consent will be sought but some of the elements of informed consent will be omitted or altered (e.g., deception). [Complete section 5.2, 5.4 and 5.6]**
- Informed consent will not be obtained – request to completely waive the informed consent requirement. [Complete Section 5.5]**

The following checkbox is for all locations EXCEPT Penn State Health and College of Medicine:

- Exempt Research at all Locations Except Penn State Health and the College of Medicine:** If you believe that the research activities outlined meet one or more of the criteria outlined in "HRP-312- Worksheet- Exemption Determination." Please verify by checking this box that if conducting an exempt research study, the consent process will disclose the following (all of which are included in "HRP-590- Consent Guidance for Exempt Research"):

Penn State affiliation; name and contact information for the researcher and advisor (if the researcher is a student); the activities involve research; the procedures to be performed; participation is voluntary; that there are adequate provisions to maintain the privacy interests of subjects and the confidentiality of the data; and subjects may choose not to answer specific questions.

If the research includes the use of student educational records include the following language in this section (otherwise delete): The parent or eligible student will provide a signed and dated written consent that discloses: the data that may be disclosed; the purpose of the disclosure; the party or class of parties to whom the disclosure may be made; if a parent or adult student requests, the school will provide him or her with a copy of the records disclosed; if the parent of a student who is not an adult so requests, the school will provide the student with a copy of the records disclosed.

Note: If this box has been checked, skip the remainder of section 5 and proceed to section 6 of this protocol. If the investigator's assessment is inaccurate, an IRB Analyst will request revision to the protocol and that an informed consent form be submitted for review and approval. Except for exemptions where Limited IRB Review (see "HRP-312- Worksheet- Exemption Determination") is required or where otherwise requested by the IRB, informed consent forms for research activities determined to be exempt without Limited IRB Review are generally not required to be submitted for review and approval by the University Park IRB.

5.2 Obtaining Informed Consent

5.2.1 Timing and Location of Consent

Describe where and when the consent process will take place.

Participants will be approached about potential participation in the study as soon as feasible following determination of eligibility and getting initial verbal consent to introduce the study to the participants. Participants could be approached prior to or shortly after (within a week) of surgery. This will occur at the Sports Medicine Clinic in State College or the Bone and Joint Clinic at the Hershey Medical Center. Subjects will be considered "enrolled" in the study after signing the informed consent. The consent form will be signed by the participants and the consenter. The signed consent form will be uploaded in REDCap. The participants will receive a copy of signed consent form via emails, mails or during in-person visit.

- In a case that in-person meeting is not possible, the consent process will be done remotely. The research staff will obtain verbal permission from the participant before sending study information via email.
- The telephone consent process follows the PSU IRB guidelines. The potential subject who is an adult and cognitively healthy person will receive a blank copy of the consent form, flyer, and a link to the introductory video. This information is provided as an email or as a hard copy prior to phone call or video conference session.
- After one or two days, a member of the study team will contact a potential participant via telephone, or video call meeting and will start the procedure of consenting, a witness will be also present with the study team member during the telephone consent discussion.
- The procedures of the study will be reviewed with the participant to ensure that the participant understands all aspects of the study. All questions and concerns will be answered prior to the end of the discussion. Time will be given for the potential participant to respond to the consent process, and give a positive response, or decline to enroll in the study. Then the subject is asked if he/she would like to participate. If yes, If the participant decides to enroll in the study the subject signature line on the consent document will be signed, dated

with time at the remote session and returned to the study team. The participant will return the signed consent form to the research staff in person or via email, fax or mail. The participant will be warned about the confidentiality risks associated with returning the signed consent form by email. The consenter and witness involved in the consent discussion will be documented in the research records.

- The consenter will add their signature to the consent form when it is received from the participant. Study activities will begin after the consent is signed by both the participant and the person obtaining consent.
- A copy of the fully executed consent form will be sent to the participant by email, mail or fax.
- The phone consent procedure should be included in the note to file used to document the informed consent process in the research record or medical record.

